1. Face Validity will be established based on interpretation of qualitative interview data of caregiver, care-recipient, OCM rater, and EAP panel member responses regarding the relevance of the tasks and coding method. We will use Grounded Theory, a systematic and rigorous set of principles for text interpretation developed by Strauss and Corbin (1998) to interpret qualitative data. During an “open coding” phase, meaningful statements that convey discrete concepts and ideas will be identified and allocated a code that maintains the meaning of the original expression as closely as possible. The constant comparative method of analysis will be used to continually refine the interview and coding procedure. This method involves an iterative process of making comparisons at each level of analysis (data with data, data with codes, codes with categories, etc.) throughout data collection and analysis. This process allows investigators to continuously modify and refine coding and create categories as data is being collected and analyzed. After the initial round of coding, all interviews will be recoded to ensure that the final codes are applied equally to all interviews. The codes will be grouped together into higher-level categories and ultimately distilled into the main themes of the research. Over the course of the process, a record of the process of idea generation, analyses, questions and hypothesized theoretical understandings will be maintained. Our initial hypothesized understanding is based on literature from CBT couples and family therapy, Expressed Emotion, Emotion Focused Therapy, and Attachment Theory ,
2. Concurrent Validity will be established by examining the correlation between the OCM V-4 summary scores and the Kansas Marital Conflict Scale (KMCS), a self-report measure designed to assess interpersonal difficulties. Due to the small sample size, we will use Spearman’s correlation coefficient. We anticipate OCM V-4 scores to be moderately to highly correlated with the KMCS.
3. Convergent Validity will be established by examining the correlation between the OCM V-4 summary scores and constructs that are anticipated to be different but related to interpersonal difficulties. We anticipate OCM V-4 scores to be moderately correlated with HABC Monitor behavioral/psychological and caregiver quality of life subscales, Zarit Burden, PHQ-9 rated depression, and GAD-7 rated anxiety.

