4. Discriminant Validity will be established by examining the correlation between the OCM V-4 summary score and variables anticipated to be unrelated or less related to interpersonal difficulties (e.g. HABC Monitor cognitive and functional subscales, education, SES, religion). We anticipate OCM V-4 scores to show no or small correlations with these variables. We will also compare the mean OCM V-4 summary scores of caregivers who experience significant caregiver burden or depression (PHQ-9>5 or Zarit Burden Scale >9) to those who do not report significant burden and depression to determine whether the

identified interpersonal variables differentiate caregivers who are experiencing significant distress from those who are not.

5. Criterion Validity will be established by examining inter-rater reliability of the trainee's coding with those of the PI as the Criterion Coder. We anticipate that the trainees will show good reliability with the Criterion Coder.
6. Content Validity will be established by calculating a content validity ratio to analyze the EAP's evaluation of each item in the OCM as "essential," "useful, but not essential," or "not necessary."

Dyad Perceived Feasibility and Utility of Treatment: Following treatment, research staff will assess caregivers with the KMCS, PHQ-9, GAD-7, Zarit burden scales and conduct semi-structured interviews with caregivers (and care-recipients, when possible) to assess reactions to the treatment, perceived benefit, feedback how to make the treatment more relevant, and willingness to refer others to the treatment. We will summarize retention rates and conduct descriptive analyses of the primary outcomes (mean with SD, median with IQR, boxplot, and frequency table) at baseline and post treatment. Within group effect sizes (Cohen's d) will be calculated. The constant comparative method of analysis will be used to analyze qualitative interview data.

Clinician Perceived Feasibility and Utility of Treatment: Research staff will conduct semi-structured interviews with family therapists to gather data on their experience providing the treatment and potential modifications to both the treatment and the OCM based on therapist experience providing the family intervention. Research staff will record and transcribe all interviews for qualitative analysis. The constant comparative method of analysis will be used to analyze qualitative interview data.

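### Items 2 to 4 of the OCM V-4 validity analysis rest on correlations in 15 dyads with no interval and no item 3 versus item 4 contrast, so point estimates cannot separate small from moderate

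*Combined protocol and SAP*

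**What the plan says.** All of this is in the Combined protocol and SAP, Data Analysis, Assessment of Validity of OCM V-4.

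- Item 2: "Concurrent Validity will be established by examining the correlation between the OCM V-4 summary scores" and the KMCS, with a moderate to high correlation anticipated. Spearman's coefficient is chosen "Due to the small sample size". Within items 2 to 4 this is the only mention of sample size, and it settles the type of coefficient, not its precision.
- Item 3 (convergent): "We anticipate OCM V-4 scores to be moderately correlated with HABC Monitor behavioral/psychological and caregiver quality of life subscales", and likewise with Zarit, PHQ-9 and GAD-7.
- Item 4: "Discriminant Validity will be established by examining the correlation" of the summary score with "variables anticipated to be unrelated or less related to interpersonal difficulties". The examples are "HABC Monitor cognitive and functional subscales, education, SES, religion". The expectation reads: "We anticipate OCM V-4 scores to show no or small correlations with these variables".

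OCM Development (OCM Versions) and Training both give 15 dyads as the OCM V-4 sample. None of the three items gives a numeric meaning for small or moderate, a confidence interval, or a contrast between an item 3 and an item 4 coefficient.

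**The concern.** Discriminant evidence is an argument that some correlations are weak, and weaker than others. Both parts need precision. A low coefficient in 15 dyads may come from a weak relation or from a moderate one that sampling error has hidden. A coefficient of 0.35 with a supposedly unrelated variable may be chance. Putting the two sets of coefficients next to each other does not show that one is lower unless the difference carries its own uncertainty.

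At stake is what the pilot says about the OCM and carries into later work. Read from point estimates alone, the results could be reported as having established discriminant validity when they have not, or could cast doubt on an instrument that behaves as expected.

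**Working it through.** The plan states no power, interval width or target correlation, so there is no figure of its own to reproduce.

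**Inputs.** n = 15 (OCM Versions; Training). Spearman's coefficient (named in item 2, assumed for items 3 and 4). Assumptions not in the documents: small is below 0.3 in absolute value, moderate is 0.3 to 0.5, and two comparison variables correlate 0 to 0.5 with each other.

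**1. Interval for one coefficient.** Fisher z with the Bonett-Wright standard error: z = atanh(r), SE = sqrt((1 + r²/2)/(n - 3)), limits = tanh(z ± 1.96 SE).

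| Observed r | z | SE | 95% CI |
|---|---|---|---|
| 0 | 0 | sqrt(1/12) = 0.289 | -0.51 to 0.51 |
| 0.1 | 0.100 | sqrt(1.005/12) = 0.289 | -0.44 to 0.58 |
| 0.3 | 0.310 | sqrt(1.045/12) = 0.295 | -0.26 to 0.71 |
| 0.5 | 0.549 | sqrt(1.125/12) = 0.306 | -0.05 to 0.82 |

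The interval around 0.1 contains 0.5, and the interval around 0.5 contains 0.1. Whatever value is observed, the larger limit is at least 0.51 in absolute value. An observed 0 would need n = 16 to exclude 0.5 (tanh(1.96/sqrt(13)) = 0.496) and n = 44 to exclude 0.3 (tanh(1.96/sqrt(41)) = 0.297).

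**2. How often a point estimate lands on the wrong side of 0.3.** Simulated normal samples, n = 15:
- a true 0 gives an absolute value of 0.3 or more in about 28%;
- a true 0.5 gives less than 0.3 in about 22% (20% if 0.5 is the Spearman rather than the Pearson value);
- a true 0.7 gives less than 0.3 in only 3 to 4%, so a gross violation would usually show.

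**3. One item 3 variable against one item 4 variable.** If both true correlations are 0.4, so that nothing discriminates, the pair still looks discriminant (item 3 at 0.3 or more, item 4 below 0.3, both in absolute value) in about 18 to 24% of samples. If the expected ordering is true, the sample reverses it this often:

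| True item 3 v item 4 | Reversed, absolute values | Reversed, signed values |
|---|---|---|
| 0.5 v 0.1 | 16-19% | about 7-15% |
| 0.4 v 0.1 | 25-28% | about 15-22% |
| 0.3 v 0.1 | 35-37% | about 25-31% |

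The ranges cover a correlation of 0 to 0.5 between the two variables.

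**4. What a direct comparison would deliver.** Zou's interval for two dependent correlations combines the limits from step 1 with k, the estimated correlation between the two coefficients. Take observed 0.5 and 0.1, with the two variables correlating 0.3, which gives k = 0.277:
- lower limit: 0.4 - sqrt(0.551² + 0.483² - 2 × 0.277 × 0.551 × 0.483) = 0.4 - 0.624 = -0.22;
- upper limit: 0.4 + sqrt(0.318² + 0.536² - 2 × 0.277 × 0.318 × 0.536) = 0.4 + 0.542 = 0.94.

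The interval is -0.34 to 1.03 if the two variables are uncorrelated and -0.13 to 0.87 if they correlate 0.5. Two-sided power to detect a true 0.5 v 0.1 is about 20% (16 to 25%).

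**The case against.** The study calls itself a first step and a pilot. Item 4 is one of six validity strands, all of which use the same verb, and it sits beside reliability and qualitative work. The plan says correlations will be examined. It does not say that conclusions will rest on point estimates alone, and silence about intervals in a short protocol is not a commitment to leave them out. The thresholds of 0.3 and 0.5 are supplied here, not by the plan. Intervals at this size will mostly show that little can be concluded.

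The set of coefficients read together also says more than any single pair. In simulations with five item 3 variables and four item 4 variables (true item 4 correlations of 0.1), the mean absolute item 3 coefficient exceeded the item 4 mean in 67 to 71% of samples at a true item 3 value of 0.3, 79 to 85% at 0.4 and 89 to 95% at 0.5.

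Most of this stands, and it limits the weight of the point. It does not remove it. The wording promises more than 15 dyads can support, and less related has no analysis attached. Half-widths near 0.5 blur any reasonable boundary between small and moderate, so the conclusion does not hang on the exact cut-offs. That the intervals will be wide is the information a reader of the pilot needs.

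**Conclusion.** The concern holds as a minor point. At n=15, under the assumed meanings of small and moderate, a point estimate cannot tell one from the other, and the plan provides neither an interval nor the comparison that its own wording calls for. The simulated rates also assume normal data.

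The documents do not support several stronger readings that a reader might infer:

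- **That the no-or-small expectation is a pass rule, or that a wrong decision would follow.** It is an expectation with no cut-off. Wave 2 dyads go on to Family Therapy whatever item 4 shows, and V-4 is the last OCM version listed. For the same reason the plan should not be judged by whether every coefficient falls as anticipated, and an interval that reaches moderate values need not trigger a fixed verdict. At n=15 every interval does so.
- **That correlating religion is an error.** It is one example in a list, and the documents do not show how it is coded.
- **That the comparison of distressed with non-distressed caregivers in item 4 is a defect.** Its purpose is stated there. Which heading it sits under is a matter of labelling.
- **That the sample must grow.** Nothing in a pilot of this kind requires item 4 to be conclusive.

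**What to change.** 1. In items 2 to 4, replace *will be established* with *will be preliminarily estimated*.
2. Report the coefficients from the three items side by side, each with a 95% confidence interval suited to Spearman's coefficient, for example Fisher z with the Bonett-Wright standard error.
3. Base any statement that a variable is less related on one difference named in advance, with a 95% interval for dependent correlations. HABC Monitor behavioral/psychological minus HABC Monitor cognitive is a natural choice, because the Measures section describes both as domains of one caregiver assessment.

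The cost is a change of wording and a few lines of analysis. Sample size, recruitment and measures are unchanged. The downside is that the intervals will be wide, including the one for the difference, and the pilot's claims will be more modest.
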